6.7 Concomitant Medication Assessments

The study coordinator or designee will record concomitant medication history in the source document and eCRF. Changes in phosphate binder and calcium supplement therapy will be collected in the eCRFs.

6.8 Removal of Subjects from the Study or Study Drug

The investigator may withdraw a subject from the study for any of the following reasons:

- A major protocol deviation occurs;
- A serious or intolerable AE occurs;
- A clinically significant change in a laboratory parameter occurs;
- The sponsor or investigator terminates the study;
- The subject requires more than four dose reductions;
- The subject requests to be discontinued from the study;
- If the investigator believes it is no longer in the best interests of the subject to continue
- A subject experiences more than a 100% increase in plasma iPTH after 26 weeks of treatment from pre-treatment baseline; or
- A subject exhibits plasma iPTH above 600 pg/mL on consecutive visits (if at least 2 weeks apart) after 12-weeks of treatment.

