3.2 Rationale for Study Design and Control Group

EirGen is developing CTAP101 Capsules for the treatment of SHPT in pediatric patients with stages 3 or 4 CKD and VDI. The active ingredient in CTAP101 Capsules is calcifediol, which is formulated as ER capsules for oral administration.

The present study is designed to compare the efficacy of CTAP101 Capsules to matching placebo with regard to reducing mean plasma iPTH levels by at least 30% from pre-treatment baseline in pediatric patients with stage 3 or 4 CKD and VDI. The study will also examine the safety and tolerability of CTAP101 Capsules compared to placebo. This adequate and well-controlled, randomized and double-blind study provides the best means to evaluate efficacy, safety and tolerability of CTAP101 Capsules because no therapy has yet been approved by the FDA to treat elevated iPTH levels associated with low serum total 25-hydroxyvitamin D levels in pediatric CKD patients. In other studies conducted in adult subjects with stage 3 or 4 CKD and SHPT, administration of placebo therapy for 26-weeks has not been shown to result in untoward effects [Coyne 2006; Coburn 2004]. However, since iPTH values >900 pg/mL have been associated with increased risk of fracture in hemodialysis patients [Jadoul 2006], subjects will be terminated from this study for confirmed iPTH levels >900 pg/mL.

The starting dose of 30 mcg per day is based on the results from two phase 3 studies (CTAP101-CL-3001 and CTAP101-CL-3002) conducted in adults with SHPT, stage 3 or 4 CKD and VDI. Data from these studies demonstrated that steady-state serum 25-hydroxyvitamin D₃ levels were reached after 12 weeks of treatment at daily doses of 30 or 60 mcg of CTAP101 Capsules. Accordingly, upward dose titration is not allowed in the present study until after 12 weeks, when subjects receiving the initial dose of CTAP101 Capsules have attained steady-state blood levels of serum total 25-hydroxyvitamin D. A 26-week treatment period was selected for this study to ensure that steady-state will be attained in subjects who undergo upward dose titration at the beginning of treatment week 13.

Previous PK analyses in adult CKD patients have determined that the $t_{1/2}$ of serum 25-hydroxyvitamin D₃ is approximately 30 days (CTAP101-CL-2008). Consequently, the post-dosing FU period of 6-weeks should be sufficient for determining the $t_{1/2}$ in pediatric patients.

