5.7 Blinding

An IRS will provide study treatment group assignments (using a computer-generated randomization code provided by the IRS vendor) and dosing adjustments. An independent, unblinded DSMB will oversee the IRS and verify the appropriateness of all dosing adjustments, and monitor subject safety and the effectiveness of CTAP101 Capsules at regular intervals. Members of the DSMB will also conduct periodic reviews of study conduct to verify that all required data are captured to a sufficiently high degree (>95%) and within specified time frames (usually within 5 days), and to promptly recommend appropriate corrective actions to address any noted deficiencies, in an effort to minimize missing data. Specific responsibilities and activities of the DSMB will be defined in the charter ratified at the pre-study organizational meeting. These responsibilities will include the completion of an interim analysis of the repeated-dose PK data obtained during treatment week 12 in Cohort 1 to justify a starting dose for Cohort 2.

All subjects, site research staff and sponsor will be blinded as to whether a given subject is in the CTAP101 Capsules or placebo treatment group until after database lock or until the decision to break the blind is determined (eg, as a result of an emergent event, SUSAR). When the primary investigator determines that knowledge of treatment group assignment is required for medical management of an individual subject, the sponsor will be contacted immediately. The blind for the subject will be broken using the IRS system.

Further, all subjects, site research staff and sponsor will be blinded to the administered treatments and plasma iPTH, serum total 25-hydroxyvitamin D, and serum 25-hydroxyvitamin D₃ laboratory data until the last subject completes 26 weeks of treatment. Unblinded data will be provided to all study sites when the final clinical study report becomes available.

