6.5 Dispensing Study Drug

As described in [Section 5.6](#) Method of Assigning Subjects to Treatment Groups, the IRS will assign the study drug bottle(s) to the subject at the time of randomization (Visit 3) and at Visit 13. The study coordinator (or designated site personnel) will obtain the study drug assignment from the IRS for each subject and dispense the appropriate drug.

Subjects and their appointed guardians are to be instructed NOT to take study drug if it appears discolored or damaged. Subjects are to be advised that the study drug is to be stored at room temperature, 15-30°C (59-86°F). Protect from light and heat.

Subjects will receive a sufficient number of bottles of study drug at visits 3 and 13. Some bottles will contain CTAP101 Capsules and others may contain a matching placebo, dependent on

individual subject dose assignment. Throughout the treatment period the number of capsules remaining in the bottle will be counted by the investigator or designee and recorded on the drug accountability log at Visits 13 and 22. The bottles will then be returned to the subject. Prior to dispensing new bottle(s) of study drug, the coordinator will collect the previous bottle(s) of study drug. See [Section 5.3 Selection and Timing of Dose for Each Subject](#) for further details of drug dispensation.

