7.2 Treatment Period (Weeks 1-26)

7.2.1 Visits 4-10 (Days 8-71)

- May occur ± 3 days of scheduled day
- AE assessment
- Concomitant medications

- VS measurements
- Blood samples drawn for:
 - Chemistry (partial panel)
 - Plasma iPTH
 - Serum total 25-hydroxyvitamin D

7.2.2 *Visits 11-12 (Days 83-84)*

- Must occur on the scheduled days
- AE Assessment
- Concomitant medications
- VS measurements
- Blood samples drawn for all subjects at 0 (pre-dose), 6 and 12 hours and additionally, only for subjects assigned to intensive PK evaluation, at -2, 2, 4 and 8 hours after dosing on Day 83 for:
 - Chemistry (partial panel)
 - Serum 25-hydroxyvitamin D₃, [REDACTED]
- Blood samples drawn at 24 hours ±4 hours before dosing on Day 84 for:
 - Chemistry (partial panel)
 - Serum 25-hydroxyvitamin D₃, [REDACTED]

7.2.3 *Visit 13 (Day 85):*

- Must occur on the scheduled day
- Urine pregnancy (for females of childbearing potential)
- AE assessment
- Concomitant medications
- Urine pregnancy (only for females of childbearing potential)
- VS measurement
- Urine chemistry and urinalysis
- Blood samples drawn at 48 hours ±4 hours before dosing for:
 - Chemistry (full panel) and hematology
 - Plasma iPTH
 - Serum total 25-hydroxyvitamin D
 - Serum 25-hydroxyvitamin D₃, [REDACTED]
 - [REDACTED]
- Drug accountability
- Patient reported palatability and acceptability

- Dispense assigned bottles of study drug

7.2.4 *Visits 14-21 (Days 92-169)*

- May occur ± 3 days of scheduled day
- Visits 14 and 16 are required only for subjects who underwent upward dose titration at visit 13
- AE assessment
- Concomitant medications
- VS measurements
- Blood samples drawn for:
 - Chemistry (partial panel)
 - Plasma iPTH
 - Serum total 25-hydroxyvitamin D

7.2.5 *Visit 22 (Day 183):*

- Must occur on the scheduled day
- Urine pregnancy (only for females of childbearing potential)
- AE assessment
- Concomitant medications
- VS measurements
- Urine chemistry and urinalysis
- Blood samples drawn for:
 - Chemistry (full panel) and hematology
 - Plasma iPTH
 - Serum total 25-hydroxyvitamin D
 - Serum 25-hydroxyvitamin D₃, [REDACTED]
 - [REDACTED]
- Patient reported palatability and acceptability
- Drug accountability

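### The high-iPTH withdrawal rules in Section 6.8 need reconciling: the 100% rule starts only when treatment has ended, and both rules rest with an investigator who is blinded to iPTH, with no notification route written.

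*Combined protocol and SAP*

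**What the plan says.** Section 6.8 opens with "The investigator may withdraw a subject from the study for any of the following reasons". Two of the listed reasons concern rising iPTH:

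- "A subject experiences more than a 100% increase in plasma iPTH after 26 weeks of treatment from pre-treatment baseline"
- "A subject exhibits plasma iPTH above 600 pg/mL on consecutive visits (if at least 2 weeks apart) after 12-weeks of treatment"

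Section 7.2 defines the treatment period as weeks 1 to 26, with Visit 22 on Day 183 as its last visit. On drug supply, Section 6.5 states: "Subjects will receive a sufficient number of bottles of study drug at visits 3 and 13". No later dispensing is scheduled.

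On who may see the results, Section 5.7 states that "all subjects, site research staff and sponsor will be blinded to the administered treatments and plasma iPTH" and the vitamin D results, until every subject has finished the 26 weeks. Sites receive unblinded data only with the final study report. Table 2 marks plasma iPTH as a blinded test.

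The rationale in Section 3.2 contains a third high-iPTH rule: "subjects will be terminated from this study for confirmed iPTH levels >900 pg/mL". It does not appear in the Section 6.8 list.

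**The concern.** A withdrawal rule needs three things: a time at which it can act, a person who holds the triggering result, and a single statement of what must happen. The 100% rule lacks the first. Both iPTH rules in Section 6.8 lack the second on the face of the protocol. The 900 pg/mL rule sits only in a rationale section, with nobody named to apply it, and is worded as mandatory where Section 6.8 is discretionary.

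Two things are at stake. One is protection: this is a placebo-controlled trial in children, and Section 3.2 itself gives fracture risk as the reason for the 900 pg/mL level. The other is the blind. If sites have to improvise, the obvious improvisation is to ask for iPTH values, and iPTH is the primary outcome variable.

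**Working it through.** **Timing.** Inputs are the visit days in Section 7 and Appendix 1, with Day 1 (Visit 3) as the first treatment day.

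- Completion of 12 weeks: 12 × 7 + 1 = Day 85. This reproduces Visit 13.
- Completion of 26 weeks: 26 × 7 + 1 = Day 183. This reproduces Visit 22.
- Dosing days in the period: 26 × 7 = 182, that is, Days 1 to 182.

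The scheduled iPTH samples from the end of treatment onward are:

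| Visit | Day | Completed weeks, (day − 1)/7 | Who is sampled | What the 100% rule could still do |
|---|---|---|---|---|
| 22 | 183 | 26 | All | Remove from follow-up only |
| 24 | 197 | 28 | Second-PK subset only | Remove from follow-up only |
| 28/ET | 225 | 32 | All | Nothing: participation ends here |

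The 100% rule can therefore stop study drug on none of the 182 dosing days. For a child outside the second-PK subset, Visits 23 to 27 are not required. Removal at Day 183 could then affect only the final visit, 225 − 183 = 42 days later.

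The 600 pg/mL rule does not share this defect. It opens at Day 85, and iPTH is sampled through to Day 183, with the last three treatment visits nominally 14 days apart (Days 155, 169 and 183). Its timing works.

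**Who holds the result.** The relevant sections, side by side:

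| Question | Section | Answer |
|---|---|---|
| Who decides on withdrawal? | 6.8 | The investigator, at discretion |
| Does the investigator see iPTH? | 5.7, Table 2 | No |
| Who is unblinded? | 5.3, 5.7, 10.8 | The DSMB, including its medical monitor |
| What are they asked to do? | 5.3, 5.7, 10.8 | Oversee the IRS and dose adjustments, monitor safety and effectiveness, check data capture, carry out interim analyses |
| How do dose reductions for low iPTH reach the site? | 5.4 | Through the IRS |
| How does a high-iPTH criterion reach the site? | – | Not stated |

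The protocol thus has a blind-preserving route for over-suppression of iPTH and none written for rising iPTH.

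**Consistency of the levels.** Section 6.8 uses 600 pg/mL on consecutive visits, after week 12, as a reason for which withdrawal is permitted. Section 3.2 uses a confirmed value above 900 pg/mL, with no start time, as a reason for which termination is required. Section 6.8 does not mention the second rule.

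**The case against.** The best defence is that the trial has an unblinded DSMB which reviews safety and effectiveness regularly, and that its detailed duties are deferred to a charter. The charter may well say who acts on a high iPTH. This stands as a limit on the finding: one can say that the protocol states no route, not that none exists.

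A second defence is that Section 6.8 already reaches termination through blinded iPTH in one case. Needing more than four dose reductions is a listed reason, reductions run through the IRS, and low iPTH is one of their criteria. This also stands. It shows that the mechanism is available, and that what is missing is wording for the high-iPTH items.

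The general reasons in Section 6.8 (a clinically significant laboratory change, the subject's best interests) help less, because a judgement on iPTH cannot be made from a result that is not seen. Emergency unblinding under Section 5.7 reveals treatment, not iPTH, and needs a trigger.

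A reader might go on to infer four stronger things, none of which the documents support:

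- *That a doubling of iPTH triggers nothing during treatment.* An active-arm child whose iPTH has not fallen by 30% at week 12 is titrated upward if calcium, phosphorus and 25-hydroxyvitamin D allow, and the DSMB monitors safety throughout.
- *That the gap can be sized as the distance from a doubled entry-floor value to 600 pg/mL.* No upper iPTH limit is set at entry, so the distance depends on baseline and is nil at 300 pg/mL (2 × 300 = 600). The 600 rule also starts only after week 12.
- *That the primary endpoint is materially affected.* The 100% rule first applies on Day 183, when the efficacy assessment period is ending. A child persistently above 600 pg/mL could be a 30% responder only with a baseline above 600/0.7 ≈ 857 pg/mL, so almost all would be non-responders in any case.
- *That 600 and 900 pg/mL contradict each other.* A discretionary level and a higher mandatory level can coexist as tiers. The defect is that Section 6.8 omits one of them.

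**Conclusion.** The point holds as an internal inconsistency that should be corrected. Three parts are established from the text:

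1. The 100% rule takes effect only on completion of treatment, so it can remove a child from follow-up but never from study drug.
2. The 100% rule and the 600 pg/mL rule are both assigned to an investigator who is blinded to iPTH, and the protocol gives no route by which the site would learn that either is met.
3. The mandatory 900 pg/mL termination in Section 3.2 is absent from Section 6.8.

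Confidence is high on the first and third parts. The second is certain as a statement about the protocol and conditional on the charter as a statement about the trial. The timing defect is confined to the 100% rule. It would be too strong to say that the rules cannot be made to work, or that the iPTH blind must be broken to apply them: the IRS and the unblinded monitor could deliver an instruction without a value. The size is that of a safeguard with no effect on dosing and of two others whose operation is unspecified. No effect on power or on the primary comparison is claimed.

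**What to change.** Reconcile Sections 3.2, 5.7, 6.8 and 7.2 on three matters: the time point of the 100% rule relative to the 26-week treatment period, the set of iPTH thresholds, and which of them are mandatory or discretionary. The values and time points are for the sponsor's clinicians to decide; none is proposed here.

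State in Section 6.8 that the high-iPTH checks run through the IRS and the unblinded DSMB monitor already used for iPTH-based dose reductions, so that the site receives only an instruction and the iPTH blind is kept. If the DSMB charter already provides this, cite it in Section 6.8; if not, add matching text to the charter.

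The cost is protocol and charter wording, with the checks added to the IRS instructions. No new samples or visits are needed to route the existing rules, and both the IRS and the unblinded monitor are already in place.

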6.9 Appropriateness of Measurements

Reduction in plasma iPTH is an accepted marker for improvement of SHPT in the CKD population. The efficacy of CTAP101 Capsules will be determined by comparing the effect of CTAP101 Capsules to that observed with placebo to lower elevated iPTH levels and to

normalize vitamin D levels. Pre- and postdose averages will be used to minimize the effect of any intrasubject and interassay variability. The post-dose average will be obtained over the last six-weeks of treatment (visits 19-22) to allow subjects to achieve steady state serum 25-hydroxyvitamin D levels.

AEs, serum calcium and phosphorus have been used to assess safety of vitamin D compounds and will be monitored in this study. The safety and tolerability of CTAP101 Capsules will be determined by comparing each active group to placebo.

7 STUDY ACTIVITIES

7.1 Screening Period

7.1.1 *Visit 1 (Day -70 to -63)*

- AE Assessment
- A signed ICF will be obtained from the subject prior to any study related procedures
- Review of inclusion/exclusion criteria, including eGFR measurement
- Medical history and demographics: date of birth, gender, race, ethnicity, cause and date of CKD. A complete medical history, including alcohol, tobacco and nicotine-containing product use histories and method of contraception, as appropriate, will be recorded
- Medication History: All prescription and over the counter medication usage for the 28 days prior to visit 1 will be recorded
- General PE (including weight, height and BMI)
- VS measurements
- Urine chemistry
- Blood samples to be drawn prior to dosing and washout (if required):
 - Chemistry (full panel) and hematology
 - Plasma iPTH
 - Serum total 25-hydroxyvitamin D
- Urine pregnancy test (only for females of childbearing potential)
- Washout assessment: Subjects who are taking any vitamin D and/or bone metabolism therapy, including vitamin D supplements ($>1,700$ IU/day of ergocalciferol or cholecalciferol), will discontinue or reduce therapy to ≤ 1700 IU/day for the duration of the study. Subjects taking more than 1000 mg/day of elemental calcium will discontinue or reduce therapy for the duration of the study.
 - If washout is not required proceed to visit 3.
 - If washout is required, proceed to visit 2 after completion of at least 8 weeks of washout.

If the screening values do not meet study entry criteria after visit 1, subject may receive supportive care per the investigator's discretion and be retested once. If values do not fall within study entry criteria on retest, the subject will be considered a screen failure and be withdrawn from the study. Only the screening test(s) that did not meet entry criteria at visit 1 are required to be re-drawn and meet entry criteria at the time of the visit 1 retest.

7.1.2 *Visit 2 (Day -7 to -1)*

This visit is only applicable for subjects requiring washout. Subjects requiring washout will need to undergo visit 2 to confirm study entry laboratory values meet or continue to meet study entrance criteria.

- Review of inclusion/exclusion criteria

- Concomitant medications
- AE assessment
- VS measurements
- Blood samples will be drawn for the following analyses:
 - Chemistry (full panel) and hematology
 - Plasma iPTH
 - Serum total 25-hydroxyvitamin D

7.1.3 Visit 3 (Day 1)

Subjects will need to confirm study entry laboratory values continue to meet study entrance criteria for serum calcium, phosphorus, total 25-hydroxyvitamin D, and plasma iPTH. This visit should occur after screening values from visit 1 (visit 2 for subjects requiring washout) meet study entry criteria.

- Review of inclusion/exclusion criteria
- Concomitant medications
- AE assessment
- General PE (including weight, height and BMI)
- VS measurements
- 12-lead ECG
- Urine chemistry and urinalysis
- Blood samples will be drawn for the following:
 - Chemistry (partial panel)
 - Plasma iPTH
 - Serum total 25-hydroxyvitamin D
 - Serum 25-hydroxyvitamin D₃, [REDACTED]
 - [REDACTED]
- Urine pregnancy (only for females of childbearing potential)
- Randomization of subject
- Dispense assigned bottles of study drug with dosing instructions

7.2 Treatment Period (Weeks 1-26)

7.2.1 Visits 4-10 (Days 8-71)

- May occur ± 3 days of scheduled day
- AE assessment
- Concomitant medications

- VS measurements
- Blood samples drawn for:
 - Chemistry (partial panel)
 - Plasma iPTH
 - Serum total 25-hydroxyvitamin D

7.2.2 *Visits 11-12 (Days 83-84)*

- Must occur on the scheduled days
- AE Assessment
- Concomitant medications
- VS measurements
- Blood samples drawn for all subjects at 0 (pre-dose), 6 and 12 hours and additionally, only for subjects assigned to intensive PK evaluation, at -2, 2, 4 and 8 hours after dosing on Day 83 for:
 - Chemistry (partial panel)
 - Serum 25-hydroxyvitamin D₃, [REDACTED]
- Blood samples drawn at 24 hours ±4 hours before dosing on Day 84 for:
 - Chemistry (partial panel)
 - Serum 25-hydroxyvitamin D₃, [REDACTED]

7.2.3 *Visit 13 (Day 85):*

- Must occur on the scheduled day
- Urine pregnancy (for females of childbearing potential)
- AE assessment
- Concomitant medications
- Urine pregnancy (only for females of childbearing potential)
- VS measurement
- Urine chemistry and urinalysis
- Blood samples drawn at 48 hours ±4 hours before dosing for:
 - Chemistry (full panel) and hematology
 - Plasma iPTH
 - Serum total 25-hydroxyvitamin D
 - Serum 25-hydroxyvitamin D₃, [REDACTED]
 - [REDACTED]
- Drug accountability
- Patient reported palatability and acceptability

- Dispense assigned bottles of study drug

7.2.4 *Visits 14-21 (Days 92-169)*

- May occur ± 3 days of scheduled day
- Visits 14 and 16 are required only for subjects who underwent upward dose titration at visit 13
- AE assessment
- Concomitant medications
- VS measurements
- Blood samples drawn for:
 - Chemistry (partial panel)
 - Plasma iPTH
 - Serum total 25-hydroxyvitamin D

7.2.5 *Visit 22 (Day 183):*

- Must occur on the scheduled day
- Urine pregnancy (only for females of childbearing potential)
- AE assessment
- Concomitant medications
- VS measurements
- Urine chemistry and urinalysis
- Blood samples drawn for:
 - Chemistry (full panel) and hematology
 - Plasma iPTH
 - Serum total 25-hydroxyvitamin D
 - Serum 25-hydroxyvitamin D₃, [REDACTED]
 - [REDACTED]
- Patient reported palatability and acceptability
- Drug accountability

